12 SAFETY EVALUATION

All safety evaluations will be conducted on the Safety population at the following time points.

- Concomitant medication will be summarized for the study period for all enrolled subjects.
- AEs will be summarized for the study period for all enrolled subjects.
- Vital signs will be summarized at Baseline, Stage 2 Weeks 2, 4, 8, 12, 16, 20, 24, and nominal visits in Stage 3 and Stage 4 will be summarized.
- Electrocardiograms will be summarized at Baseline, Stage 2 Weeks 4, 24, and nominal visits in Stage 3 and Stage 4 will be summarized.
- Lab tests will be summarized at Baseline, Stage 2 Weeks 2, 4, 8, 12, 16, 20, 24, and nominal visits in Stage 3 and Stage 4 will be summarized.
- Antibodies to teduglutide and ECP will be summarized at Baseline, Stage 2 Weeks 12, 24, and nominal visits in Stage 3 and Stage 4 will be summarized.
- 48-hour oral fluid intake and 48-hour urine output will be summarized at Baseline, Stage 2 Weeks 2, 4, 8, 12, 16, 20, 24, and nominal visits in Stage 3 and Stage 4 will be summarized.
- Body weight and BMI will be summarized at Baseline, Stage 2 Weeks 2, 4, 8, 12, 16, 20, 24, and nominal visits in Stage 3 and Stage 4 will be summarized.

Complete dates will be imputed from partial dates of adverse events and medications solely for the purpose of defining treatment emergence for adverse events and prior/concomitant status for medications. Dates will be defined using the hierarchy of derivations below.

Adverse event or medication start date (references to month are the month of the start date):

1. If year and month are known, and it is the month and year of the first dose date, use the first dose date.
2. If year and month are known, and it is the month and year of the informed consent, use the informed consent date.
3. If year and month are known, and the month is not the month and year of the first dose or informed consent, use the first day of the month.
4. If only year is known, and it is previous to the year of the informed consent, use June 30th of that year.
5. If only year is known, and it is the year of the informed consent, use the informed consent date.
6. Should any of the previous start dates created be after a complete stop date provided, use the stop date instead of the date that would otherwise be created.
7. Otherwise, if start date is unknown leave as missing.

Medication stop date (references to month are the month of the stop date):

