13.2 Adverse Events

Adverse events will be summarized in three categories: 1) Overall TEAEs that happened in the study, 2) TEAEs that happened in Stage 2, and 3) TEAEs that happened in Stage 3 and 4. AEs will be coded using the MedDRA. Investigator verbatim as well as preferred terms and body systems will be included in the listings, and the corresponding list of body systems, preferred terms and the verbatim terms that code to each preferred term will be presented as a preface to the listings of the AEs.

Treatment emergent AEs (TEAEs) are defined as AEs whose onset occurs, severity worsens, or intensity increases after receiving the study medication. AEs with an unknown date of onset and a stop date after the start of the study period or unknown will be included as treatment emergent AEs. Any AE with a start date equal to the date of first dose, where the time of the AE can't definitively place the start of the AE prior to the first dose, will be considered treatment emergent. If any AE records contain only partial dates, these will be handled by imputation, as described in Section 6.3. AEs which are not treatment emergent will be flagged in listings.

AEs will be summarized overall using descriptive statistics (e.g., number and percent of subjects). The number of events will also be presented except for summaries by highest category. Categories summarized will include any TEAEs, severity of TEAEs (any and highest category), investigator assessment of relationship of TEAEs to study treatment, treatment emergent serious AEs (TESAEs), severity of TESAEs, investigator assessment of relationship of TESAEs to study treatment, TEAEs leading to death, and TEAEs leading to discontinuation.

Treatment emergent AEs will be summarized using number and percentage of subjects. Subject incidence for AEs within each SOC and PT will be presented, unless otherwise specified. TEAEs will be summarized by Severity. The number of events will also be summarized except for summaries by highest category. TEAEs will be summarized by relationship to the drug, whether it is related or not related. TESAEs will be summarized. TESAE will also be summarized based on Severity as well as Relationship. Presentation by SOC and PT will present SOC sorted alphabetically and PT within SOC by descending incidence.

Summaries of TEAEs, related TEAEs, and TESAEs will also be presented by PT. These presentations will be sorted by descending incidence.

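### Start-date rule 5 classes a year-only adverse event as pre-treatment whenever first dose falls in the consent year, even if it began on treatment

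*SAP*

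**What the plan says.** Section 12 gives one list of seven start-date rules for adverse events and medications and limits their purpose: "Complete dates will be imputed from partial dates of adverse events and medications solely for the purpose of defining treatment emergence for adverse events" (and, for medications, prior or concomitant status). The rules that matter here are:

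- **Rule 1** (month and year known): "If year and month are known, and it is the month and year of the first dose date, use the first dose date".
- **Rule 5** (year only): "If only year is known, and it is the year of the informed consent, use the informed consent date".
- **Rule 6** (check against the stop date): "Should any of the previous start dates created be after a complete stop date provided, use the stop date instead".
- **Rule 7** (fallback): "Otherwise, if start date is unknown leave as missing".

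Section 13.2 defines TEAEs as "AEs whose onset occurs, severity worsens, or intensity increases after receiving the study medication". It then treats two kinds of incomplete date differently. For a wholly unknown onset: "AEs with an unknown date of onset and a stop date after the start of the study period or unknown will be included" as treatment-emergent. For a partial date: "If any AE records contain only partial dates, these will be handled by imputation, as described in Section 6.3". Section 6.3 in turn refers the reader to the safety evaluation, so the rules that apply are those in Section 12.

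Section 2.1 places Stage 1 before dosing. It has a stabilization period of 4 to 8 weeks, preceded if required by up to 8 weeks of optimization.

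**The concern.** The only job of the imputed date for an adverse event is to decide whether the event is treatment-emergent. Rule 5 anchors that decision to consent and ignores first dose. Where both fall in the same year, every year-only event of that year is given a pre-dose onset, including those that began after dosing.

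The direction of the error is anti-conservative: TEAEs can be undercounted in a study that has safety among its objectives. It also runs against the rest of the plan. An event in the month of first dose is given to treatment. So is an event on the day of first dose whose time does not settle the order, and so is an event with no onset date at all. A record that carries the year can therefore be excluded where a record that carries nothing is included.

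**Working it through.** The SAP states no figure on this point, so there is none to reproduce. The check traces the rules on an example and then sizes the exposed period.

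**1. Tracing the rules.** Illustrative subject: consent 15 January, first dose 12 March of the same year (56 days, 8 weeks). The true onset is 10 July in the first four rows and some day in the following year in the last row. No stop date is recorded.

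| Onset as recorded | Rule | Imputed start | TEAE by onset? |
|---|---|---|---|
| Month and year (July) | 3 | 1 July | Yes |
| Month and year, wrongly noted as March | 1 | 12 March | Yes |
| Year only, consent year | 5 | 15 January | **No** |
| Nothing | 7 | Missing | Yes, by the unknown-onset rule |
| Year only, following year | 7 | Missing | Yes, by the unknown-onset rule |

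Adding a stop date of 20 July to the third row changes nothing. Rule 6 acts only when the imputed start is later than the stop date, so it can move a start earlier but never later. The unknown-onset rule does not apply either: Section 13.2 sends partial dates to imputation, and rule 5 then supplies a date. Medications share rule 5 but have a further test in Section 13.8, where a stop date after first dose makes them concomitant. Adverse events with an imputed start have no such test.

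**2. Size of the exposed period.** Inputs: a Stage 1 of L days. From Section 2.1, one attempt lasts from 4 weeks (28 days) to 8 + 8 = 16 weeks (112 days). Assumptions: consent is given at the start of Stage 1, consent and event days are uniform over a 365-day year, the event falls on or after consent in the consent year, and only its year is known.

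- Pairs of consent day and event day in the year: 365 × 366 / 2 = 66,795.
- Pairs with the event on or after first dose, with n = 365 − L: n(n + 1) / 2.
- Share of consent dates with first dose in the same year: n / 365.

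| Stage 1 | n | First dose in consent year | On-treatment pairs | Share of post-consent days |
|---|---|---|---|---|
| 4 weeks | 337 | 92% | 56,953 | 85% |
| 8 weeks | 309 | 85% | 47,895 | 72% |
| 12 weeks | 281 | 77% | 39,621 | 59% |
| 16 weeks | 253 | 69% | 32,131 | 48% |

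Two full attempts at stabilization (about 32 weeks, an assumption) would give n = 141 and 10,011 / 66,795 = 15%. Within each on-treatment share, rule 5 classes every year-only event as pre-treatment by onset.

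**3. Effect on a table row.** Section 2.1 plans at least 5 subjects. One subject is then at most 1/5 = 20 percentage points.

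**The case against.** The strongest reply is that this will seldom matter. Stage 2 visits take place at Weeks 2, 4, 8, 12, 16, 20 and 24, start dates and times are listed, and Section 4 provides for data validation and discrepancy management. An event with neither day nor month should be unusual. That stands, and it governs the priority. The percentages above are shares of calendar time, not probabilities of misclassification, and they apply only once day and month are both lost.

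Several stronger readings are tempting, but the SAP does not support them:

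- **That such an event can never be a TEAE.** Worsened severity or increased intensity after dosing still qualifies it. The exclusion is by onset only.
- **That every subject is exposed.** If first dose falls in the year after consent, a consent-year event really is pre-treatment and rule 5 is right. That is so for consent after 3 December with a 4-week Stage 1, and after 10 September with a 16-week one. Worked examples with consent early in the year overstate the size.
- **That Stage 1 usually lasts 8 to 16 weeks.** Section 2.1 gives a range of durations and no typical value.
- **That a stop date well into treatment proves a treatment-emergent onset.** It shows that the event was present on treatment, not that it began there.
- **That the event disappears.** It is flagged in listings and fits the pre-treatment summary, Table 14.3.2.16. The detail tables for serious events, discontinuations and deaths (14.3.2.11, 14.3.2.13, 14.3.2.14) are not restricted to TEAEs by their titles.
- **That neighbouring gaps add to the undercount.** A year-only date after the consent year is left missing and so counts as a TEAE, although the SAP does not say how to place it by stage or onset window. The unknown-onset rule refers to a study period that the SAP does not define. If that period includes Stage 1, the error would be an overcount.

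**Conclusion.** The point holds in limited form. When consent and first dose share a calendar year, rule 5 gives the wrong answer for every year-only event that began on treatment and is not recorded as worsening. It does so in the anti-conservative direction and against the plan's own treatment of comparable doubt. The exposed period is about 85% to 48% of post-consent days in the consent year for a 4- to 16-week Stage 1, given uniform dates. The number of events affected cannot be stated, because the SAP gives no frequency of year-only onsets, and it is probably small. The 20-point shift is a ceiling: it needs exactly 5 subjects and a subject with no other event in that row. The error is one of classification, not loss of data. It is a lower-priority correction, worth making because it is cheap and the rule has no other purpose for adverse events than the one it fails.

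**What to change.** Replace rule 5, for adverse events only, with:

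> If only the year is known and it is the year of first dose, use the first dose date, unless a complete stop date precedes first dose. Use the consent date only if the consent year is earlier than the first-dose year.

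Rule 6 stays and already handles the stop-date exception. Rule 5 can remain as it is for medications, where the stop-date test in Section 13.8 gives some protection.

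On the same grid of dates, the share of on-treatment consent-year events classed as pre-treatment falls from 100% to 0% at every Stage 1 length examined. The price is the opposite error: a year-only event that began before dosing in the first-dose year becomes a TEAE unless a complete stop date before first dose is recorded. With no stop dates at all, that would apply to 337 × 28 / (66,795 − 56,953) = 96% of pre-dose consent-year days for a 4-week Stage 1, and to 253 × 112 / (66,795 − 32,131) = 82% for a 16-week one. Since year-only onsets are probably rare, this should mean a few events at most, and it errs in the conservative direction. The work is a short change of wording and a small change to the date derivation.

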13.1 Extent of Exposure

The extent of exposure is defined as the number of days on treatment, calculated as:

$$(\text{date of last dose} - \text{date of first dose}) + 1.$$

The first dose date, last dose date, and interruptions of study medication will be based on the eCRF. The extent of exposure, the number of days that the dose was administered will be summarized. The number and percentages of subject will be tabulated for extent of exposure categorized into months (<6 months, 6 – <12 months, 12 – <24 months, 24 – <30 months, >=30 months). Exposure summaries will be presented for the ITT and Safety Population.

13.2 Adverse Events

Adverse events will be summarized in three categories: 1) Overall TEAEs that happened in the study, 2) TEAEs that happened in Stage 2, and 3) TEAEs that happened in Stage 3 and 4. AEs will be coded using the MedDRA. Investigator verbatim as well as preferred terms and body systems will be included in the listings, and the corresponding list of body systems, preferred terms and the verbatim terms that code to each preferred term will be presented as a preface to the listings of the AEs.

Treatment emergent AEs (TEAEs) are defined as AEs whose onset occurs, severity worsens, or intensity increases after receiving the study medication. AEs with an unknown date of onset and a stop date after the start of the study period or unknown will be included as treatment emergent AEs. Any AE with a start date equal to the date of first dose, where the time of the AE can't definitively place the start of the AE prior to the first dose, will be considered treatment emergent. If any AE records contain only partial dates, these will be handled by imputation, as described in Section 6.3. AEs which are not treatment emergent will be flagged in listings.

AEs will be summarized overall using descriptive statistics (e.g., number and percent of subjects). The number of events will also be presented except for summaries by highest category. Categories summarized will include any TEAEs, severity of TEAEs (any and highest category), investigator assessment of relationship of TEAEs to study treatment, treatment emergent serious AEs (TESAEs), severity of TESAEs, investigator assessment of relationship of TESAEs to study treatment, TEAEs leading to death, and TEAEs leading to discontinuation.

Treatment emergent AEs will be summarized using number and percentage of subjects. Subject incidence for AEs within each SOC and PT will be presented, unless otherwise specified. TEAEs will be summarized by Severity. The number of events will also be summarized except for summaries by highest category. TEAEs will be summarized by relationship to the drug, whether it is related or not related. TESAEs will be summarized. TESAE will also be summarized based on Severity as well as Relationship. Presentation by SOC and PT will present SOC sorted alphabetically and PT within SOC by descending incidence.

Summaries of TEAEs, related TEAEs, and TESAEs will also be presented by PT. These presentations will be sorted by descending incidence.

Listings will be provided for serious adverse events (SAEs), AEs leading to death, and AEs leading to discontinuation of study drug. The listings will be sorted by subject identifier and will include gender, age, SOC, PT, reported term, start date/time, end date/time, frequency, severity, relationship, action taken, and outcome.

Pre-Treatment AEs will be summarized. These AEs will be summarized using number and percentage of subjects. Subject incidence for AEs within each SOC and PT will be presented. The number of events will also be summarized. Presentation by SOC and PT will present SOC sorted alphabetically and PT within SOC by descending incidence.

TEAEs will be summarized by time to onset (<6 months, 6 – <12 months, 12 – <24 months, 24 – <30 months, >=30 months). These AEs will be summarized using number and percentage of subjects. Subject incidence for AEs within each SOC and PT will be presented. The number of events will also be summarized. Presentation by SOC and PT will present SOC sorted alphabetically and PT within SOC by descending incidence.

One of the benefits of Teduglutide's ability to reduce PN assumption is to reduce or eliminate the risk of systemic catheter-related infections in SBS patients who are PN dependent. Adverse events that are considered to be central line systemic infections include central line infection, catheter related infection, catheter sepsis, catheter bacteraemia,

bacteraemia, and blood culture positive. These TEAEs will be presented by PT, sorted by descending incidence.

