1 INTRODUCTION AND BACKGROUND INFORMATION

2.1 Study Design

This is an open-label, multicenter, 4-stage study consisting of an optimization/stabilization period (Stage 1), a 24-week treatment period in which all subjects will receive teduglutide 0.05 mg/kg/day (Stage 2), and a long-term extension (Stages 3 and 4).

At least 5 subjects may be enrolled during the recruitment period, which ends approximately 6 months after the initiation of the study.

Main Treatment Period (Stages 1 and 2)

Stage 1 will include a screening visit; a maximum 8-week PN/I.V. optimization period (if required); and a stabilization period that demonstrates stable PN/I.V. support for a minimum of 4 weeks to a maximum of 8 weeks.

If at screening a subject does not have a stable PN/I.V. volume, defined as a 48-hour urine output within 2 to 4 L, he/she will enter the optimization period, during which the minimally tolerated stable PN/I.V. volume will be determined during a period of up to 8 weeks. If it is not possible to keep the subject adequately hydrated and nourished within the target urine output range, the minimally tolerated PN/I.V. volume will be documented.

All subjects will then enter the stabilization period, during which the target volume will be maintained for at least 4 consecutive weeks (8 weeks maximum) prior to entering the dosing period (Stage 2).

If a subject fails to maintain a stable PN/I.V. volume for at least 4 consecutive weeks, the subject may start the optimization period again, beginning with Week 2 (Visit 1.1). Those subjects who fail to stabilize after 2 attempts will not proceed further and will not be included in Stage 2.

Stage 2 will be a 24-week dosing period, during which subjects will self-administer teduglutide 0.05 mg/kg/day at home. Stage 2 will begin with baseline assessments of hydration and nutritional status once the subjects have demonstrated PN/I.V. stability for 4 to 8 weeks. At least 5 subjects will be enrolled. The on-treatment study visits will occur at Weeks 2, 4, 8, 12, 16 and 20, with the last scheduled visit at Week 24 of Stage 2.

Extension Treatment Period (Stages 3 and 4)

[figure not shown]

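### The rule for adverse events with unknown onset is tied to an undefined study period, not to first dose, so on the natural reading it counts events that ended before any drug was given

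*SAP*

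**What the plan says.** SAP Section 13.2 gives the general definition first: "Treatment emergent AEs (TEAEs) are defined as AEs whose onset occurs, severity worsens, or intensity increases after receiving the study medication". The next sentence adds as treatment-emergent "AEs with an unknown date of onset and a stop date after the start of the study period or unknown".

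Other parts of the SAP bear on the second sentence:

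- **Section 2.1 (Study Design):** "Stage 1 will include a screening visit; a maximum 8-week PN/I.V. optimization period (if required); and a stabilization period". Subjects pass through this stage before the dosing period, which is Stage 2.
- **Section 12 (Safety Evaluation):** "AEs will be summarized for the study period for all enrolled subjects". Section 6.1 counts subjects who never received study medication as enrolled.
- **Section 12, start-date imputation:** rules 1 to 5 build a date when at least the year is known. Rule 6 limits a date so created to a complete stop date. Rule 7 leaves an otherwise unknown start missing.
- **Section 13.2, later:** "Pre-Treatment AEs will be summarized". This is Table 14.3.2.16.
- **Section 13.8:** whether a medication is concomitant is judged by comparing its dates, including the stop date, with first dose.

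**The concern.** The two adjacent sentences in Section 13.2 use different reference points. The general definition turns on receipt of study medication; the unknown-onset rule turns on the start of something called the study period. If that period opens with or before Stage 1, the rule takes in events whose stop date alone proves that they were over before the first dose.

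Counting an event of uncertain timing as treatment-emergent is a sound conservative habit when it might have begun on drug. It has no such justification when the event is known to have ended earlier. An event classed this way would enter the overall TEAE summaries, and the serious-event or central-line infection tables if it were of that kind, and would be missing from the pre-treatment table. The study has few subjects and reports safety descriptively, without testing, so these counts are the safety result.

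**Working it through.** The SAP states no figure to reproduce. The check is a trace of the date rules on one test case, followed by simple arithmetic for its size.

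**Notation.** O = onset date, S = stop date, P = start of the study period, D = date of first dose.

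**Test case.** O wholly unknown, S known, P < S < D, in a subject who is later dosed.

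1. **General definition (13.2).** An event cannot begin or worsen after it has stopped, so O ≤ S < D, and the same holds for any worsening. Result: not a TEAE.
2. **Unknown-onset rule (13.2).** O is unknown and S > P. Result: TEAE.
3. **Imputation (12).** Rules 1 to 5 need at least the year, so none applies. Rule 6 acts only on a date already created, so it does not apply. Rule 7 leaves O missing. The result of step 2 stands.

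The outcome depends on what P is:

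| Reading of study period | P | Test case under the unknown-onset rule | Agrees with the general definition? |
|---|---|---|---|
| Whole study, including Stage 1 | before D | TEAE | No |
| Dosing period only | D | The case cannot arise; an event with S < D is not made a TEAE | Yes |

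**Which reading is more natural?** Section 2.1 makes Stage 1 part of the study and has a separate term for time on drug. Section 12 pairs the study period with all enrolled subjects, a group that under Section 6.1 includes the untreated. Section 13.2 summarises pre-treatment events, so Stage 1 events are collected. These favour the first row.

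**Pre-dose window, one pass through Stage 1 (limits from 2.1).**

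- Minimum: 0 weeks optimization + 4 weeks stabilization = 4 weeks.
- Maximum: 8 + 8 = 16 weeks.
- Longer if optimization is repeated, which Section 2.1 allows.

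**Effect on an incidence.** One affected subject among n adds at most 1/n. At the minimum planned n of 5, 1/5 = 20 percentage points. The increase is zero if that subject already has a TEAE with the same preferred term.

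**After the fix.** With TEAE defined as S ≥ D or S unknown, the test case has S < D and becomes pre-treatment. The window falls from 4–16 weeks to 0.

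**The case against.** The strongest reply is that the study period may mean the dosing period. Section 9 counts vials over the study period and divides by the days from first to last dose. Section 12 summarises concomitant medication for the study period, and Section 13.8 defines such medication by first dose. Section 12 also places all safety evaluations on the Safety population, which is limited to dosed subjects, and none of the three TEAE summary categories in 13.2 is Stage 1. This stands as far as it goes: the misclassification is conditional on the reading. It does not rescue the text, because a programmer cannot tell from the SAP which reading applies.

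A reader might also infer two stronger points that the SAP does not support:

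- **That start-date rule 6 contradicts the unknown-onset rule.** It does not. Rule 6 limits start dates already created; the unknown-onset rule handles starts that stay missing. They cover different states of the data.
- **That correcting the rule would make the overall and stage-specific tables reconcile.** It would not. Any TEAE without an onset date is hard to assign to a stage, including those that the corrected rule properly keeps.

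The consequences are also limited. An affected event needs a missing onset, a known stop date before first dose, and a subject who went on to be dosed. The error would overcount TEAEs and so would not hide a drug effect. Events are listed individually, and the listings of serious events and of events leading to death or discontinuation show start and end dates, so a pre-dose stop date would be visible there.

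**Conclusion.** The point holds as a minor one. On the most natural reading of an undefined term, Section 13.2 makes treatment-emergent an event that its own preceding sentence excludes, and no imputation rule repairs this. It would be too strong to say that the SAP certainly misclassifies such events, since a dosing-period meaning is possible and would leave mainly a fault of wording.

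The conclusion assumes that the study period starts at or before Stage 1. The number of affected events is not given and is probably small. The 4 to 16 weeks is the length of the exposed window, not a measure of bias. The 20 percentage points is the most that one affected subject could add to a preferred-term incidence at n = 5, and it shrinks as n grows. Counting events with an unknown stop date as treatment-emergent is properly conservative and is not in question.

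**What to change.** In the unknown-onset sentence of Section 13.2, replace the start of the study period with the date of first dose. An adverse event with unknown onset is then:

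- treatment-emergent if its stop date is on or after the date of first dose, or is unknown;
- pre-treatment if its stop date is before the date of first dose, and reported in Table 14.3.2.16.

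This matches the general TEAE definition and the first-dose anchor that Section 13.8 uses for medications. Including the day of first dose follows the approach 13.2 already takes to events starting on that day.

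The cost is one phrase in the SAP and one programming condition. Every unknown-onset event that could have begun on treatment stays a TEAE. If the dosing period was meant all along, the change only makes that explicit and settles the case of an event stopping on the day of first dose.
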